9.5.2 Food Effect and Optional Dose Proportionality

Formal statistical analysis will be performed on the PK parameters Cmax, AUC(0-last), and AUC(0-inf) to assess the presence of food effect.

Additionally, formal statistical analysis will be performed on the dose-corrected PK parameters Cmax, AUC(0-last), and AUC(0-inf) to assess dose proportionality, if two dose levels of delafloxacin Powder for Oral Suspension are administered in the same prandial state.

For both food effect and dose proportionality analysis, the PK parameters will undergo a natural logarithmic transformation and will be analysed using a mixed effects model. The model will include terms for regimen as fixed effect and subject as a random effect.

The following comparisons are of interest:

- Regimen <C or D> (delafloxacin Powder for Oral Suspension Fed) vs Regimen B (delafloxacin Powder for Oral Suspension Fasted) (assessment of food effect)
- Regimen <C or D> (delafloxacin Powder for Oral Suspension yy mg) vs Regimen X (delafloxacin Powder for Oral Suspension xx mg) (where yy mg > xx mg) (optional assessment of dose proportionality)

For the assessment of food effect, subjects will be included in the analysis if they have data for both the fed and fasted state in regimens included in the comparison above.

The adjusted means, including differences from the comparisons and their associated 90% CIs obtained from the model, will be back transformed on the log scale to obtain adjusted GMRs and 90% CIs of the ratios.

The analysis will be performed using the SAS procedure PROC MIXED. The method will be specified as Restricted Maximum Likelihood and the denominator degrees of freedom for the fixed effects will be calculated using Kenward-Roger method [4]. The following is an example of the SAS Software code that will be used:

```
PROC MIXED DATA= METHOD=REML ORDER=INTERNAL;
  CLASS TRTAN;
  MODEL LVAR = TRTAN / OUTP=PRED DDFM=KR;
  RANDOM SUBJIDN;
  ESTIMATE <relevant pairwise treatment comparisons> / CL ALPHA=0.10;
  LSMEANS TRTAN / ALPHA=0.10;
  LSMEANS=MEANS ESTIMATES=EST;
RUN;
```

- where LVAR is the natural log transformed PK parameter of interest
- SUBJIDN is the numeric subject identifier variable
- TRTAN is the numeric treatment variable for the actual treatment (i.e., prandial state or Dose) received

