8.1 Study Plan

This is a Phase 1, single centre, single part, partially randomised, open-label, relative bioavailability study in healthy subjects.

It is planned to enrol approximately 16 healthy male and healthy non-pregnant, non-lactating female subjects.

An evaluable subject for the relative bioavailability assessment will have received delafloxacin Powder for Oral Suspension (test) and the oral delafloxacin Tablet

(reference) at the same dose level, in the fasted state, and have evaluable PK and safety data to 48 hours post-dose.

An evaluable subject for the food effect assessment will have received delafloxacin Powder for Oral Suspension in the fed and fasted state, at the same dose level, and have evaluable PK and safety data to 48 hours post-dose.

It is planned to administer up to four regimens ([Table 2](#)).

Table 2 Description of Regimens

Period	Regimen	Investigational Medicinal Product	Dose	Route of Administration
1 and 2	A	delafloxacin Tablet (reference)	450 mg	Oral, Fasted
	B	delafloxacin Powder for Oral Suspension, reconstituted with orange flavoured vehicle	450 mg	Oral, Fasted
3	C	delafloxacin Powder for Oral Suspension, reconstituted with orange flavoured vehicle	450 mg or XX mg	Oral, Fed or Oral, Fasted
4 (optional)	D	delafloxacin Powder for Oral Suspension, reconstituted with orange flavoured vehicle	XX mg or YY mg	Oral, Fed or Oral, Fasted

Details of the IMPs are provided in [Section 5.2](#). The order in which regimens are dosed may be subject to change due to logistical reasons

The effect of food on the PK of a novel delafloxacin Powder for Oral Suspension formulation may be explored in Period 3 or optional Period 4, by administering IMP after a high-fat breakfast. The effect of increasing or decreasing the dose level may also be explored.

There will be an interim decision meeting after Periods 2 and 3 to review the PK and safety data for up to 48 hours post-dose from preceding periods, in order to determine the dose and prandial state for Regimen C and Regimen D (if applicable).

There will be a minimum washout of 4 days between dosing in Periods 1 and 2. The intervals between Periods 2 and 3, and Period 3 and optional Period 4, will require a minimum of 14 days, to permit the interim decision process and IMP manufacture.

The study will follow the design in [Figure 1](#).

Subjects will undergo preliminary screening procedures for the study at the screening visit (Day -28 to Day -2).

Periods 1 and 2

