Following dosing of Regimen C, there will be an interim decision meeting to review available PK and safety data, to decide whether to proceed with optional Period 4 or whether to end the study. If it is decided to end the study, a follow-up phone call will take place on Day 6 ± 1 to ensure the ongoing wellbeing of subjects. If a subject reports any AEs that present a cause for concern, they will be required to attend the clinical unit for an (unscheduled) follow-up visit. End of study is defined as completion of the last follow-up phone call or unscheduled follow-up visit. If it is decided to proceed with optional Period 4, the dose level and prandial state for Regimen D will be determined; the Investigator and Sponsor will decide whether to continue to evaluate the dose level selected for Regimen C following a high-fat breakfast, or to evaluate an alternative dose level in the fasted state.

Optional Period 4

Subjects will be admitted in the evening on the day before dosing (Day -1). Subjects will fast overnight from all food and drink (except water) for a minimum of 10 hours, and may be administered IMP on the morning of Day 1 in the fasted state (if a different dose level is selected), or approximately 30 minutes after a high-fat breakfast (if a change to prandial state is selected). Subjects will complete a written taste/palatability questionnaire individually and privately following IMP administration.

Blood and urine samples will be collected at regular intervals for PK and safety analysis, as applicable, from admission until 48 hours post-dose (Day 3), at which time subjects will be discharged from the clinical unit. A follow-up phone call will take place on Day 6 ± 1 to ensure the ongoing wellbeing of subjects. If a subject reports any AEs that present a cause for concern, they will be required to attend the clinical unit for an (unscheduled) follow-up visit; completion of the last follow-up phone call or unscheduled follow-up visit will be considered the end of the study.

Figure 1 Study Sequence

^a Subjects will be admitted to the clinical unit in the morning on the day before dosing (Day -1) in Period 1, and in the evening on the day before dosing (Day -1) in Period 3 and optional Period 4. Subjects will remain resident in the clinical unit between Periods 1 and 2; therefore, no admission procedures will be conducted for Period 2

^b Period 4 is optional

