8.2.2 Criteria for Dose Level and Prandial Status Selection

Dose level and prandial status selection for Regimen C and Regimen D (if applicable) will only be made after a complete review of all data collected from the previous dose period(s). For dose level and prandial status selection to occur, data must be available from a minimum of 12 subjects who have completed the planned PK and safety assessments up to 48 hours after dosing. If data are not available for 12 subjects, the Investigator, Scientific Lead, and Sponsor will take a decision as to whether the data available are sufficient to support the dose level and prandial status selection decision. If data in fewer subjects are used in the decision process, additional subjects will not be dosed to increase the number of subjects in the completed regimen; however, additional subjects may be enrolled to achieve the target number of subjects for subsequent regimens.

Regimens C and D will only be administered in the fed state if the selected dose level has previously been administered in the fasted state.

The following data are required:

- AEs.
- Vital signs.
- ECGs.
- Safety laboratory tests.
- Plasma concentrations of delafloxacin.
- PK parameter estimates (Cmax, Tmax, AUC(0-last), AUC(0-inf) and Frel comparisons) up to 48 hours post-dose.

The dose(s) selected for Regimen C or Regimen D (if applicable) will only be selected from the design space of 300 mg to 600 mg.

The decisions on dose level and prandial status will be made by the SAC. The decision will be documented and signed by the Investigator as per Quotient Sciences' current standard operating procedure (SOP). Evidence of the decision will be retained in the ISF.

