8.4 Subject Replacement

Withdrawn subjects may be replaced, at the discretion of the Investigator and Sponsor, with the aim of ensuring that the objectives of the trial can be met.

Replacement subjects enrolled will be dosed with the next planned regimen of the withdrawn subject, and they will not receive any regimen that the withdrawn subject has already received, with the exception of the need to increase subject numbers to obtain the minimum number of evaluable subjects required for interim decisions, and to obtain data in any other regimen that is required for a valid comparison e.g., test vs reference, fed vs fasted.

Any subject withdrawn due to an IMP-related AE will not be replaced.

Subjects withdrawing for other reasons may be replaced.

Up to 4 replacement subjects may be enrolled into the study. The maximum number of subjects that may be dosed is 20.

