15.4 Statistical Data Analysis

Statistical analysis and production of summary tables, figures, and listings for this study will be performed by Quotient Sciences using the statistical package SAS (v9.4 or more recent version).

In general terms, categorical data (including TEAEs) will be presented using counts and percentages, while continuous variables will be presented using the mean, median, standard deviation, minimum, and maximum. Additional statistics will be provided for PK-related data including coefficient of variation (CV%), geometric mean, and geometric CV%.

Descriptive summaries for all safety data (AEs, vital signs, ECGs, and safety laboratory assessments) by regimen will be provided (including changes from baseline as required).

Descriptive summaries for all PK and taste data by regimen, as applicable, will be provided.

All PK, safety, and taste data will be listed.

Formal statistical analysis will be performed on the PK parameters Cmax, AUC(0-last), and AUC(0-inf) to assess relative bioavailability. The PK parameters will undergo a natural logarithmic transformation and will be analysed using a mixed effect model, with terms for sequence and regimen as fixed effects, and subject within sequence as a random effect. Adjusted geometric mean ratios (GMRs) and 90% confidence intervals (CIs) for the adjusted GMRs for the relevant comparison (i.e., Regimen A [reference] and Regimen B [test]) will be provided, where the ratios are defined as test/reference.

Formal statistical analysis will also be performed on the PK parameters Cmax, AUC(0-last), and AUC(0-inf) to assess for the effects of food on delafloxacin Powder for Oral Suspension regimens administered at the same dose level. The PK parameters will undergo a natural logarithmic transformation and will be analysed using a mixed effect model, with terms for regimen as fixed effect, and subject as a random effect. Adjusted GMRs and 90% CIs for the adjusted GMRs for the comparison between fed and fasted regimens will be provided, where the ratios are defined as fed/fasted.

Additionally, formal statistical analysis may be performed on log-transformed, dose-corrected PK parameters Cmax, AUC(0-last), and AUC(0-inf) to assess dose proportionality, if two dose levels of delafloxacin Powder for Oral Suspension are administered in the same prandial state, using a mixed effect model, with terms for regimen as a fixed effect and subject as a random effect.

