Non-dose corrected relative bioavailability (Frel) will be calculated as follows:

$$Frel = \left\{ \frac{AUC \text{ or } Cmax \text{ (test)}}{AUC \text{ or } Cmax \text{ (reference)}} \right\} \times 100$$

Frel will be calculated using Cmax, AUC(0-last) and AUC(0-inf). If for any reason the AUC(0-inf) is not calculable then an alternative or additional AUC over a partial area may be used to calculate Frel for all subjects.

The following comparisons will be made:

- 450 mg delafloxacin Powder for Oral Suspension (test) vs delafloxacin Tablet (reference) (Regimen A)
- 450 mg delafloxacin Powder for Oral Suspension fed (test) vs delafloxacin Powder for Oral Suspension fasted (reference)

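### SAP 9.5.2 fixes Regimen B (450 mg fasted) as the food-effect comparator, so a Regimen D fed at a non-450 mg dose would be compared across doses, against the protocol's same-dose rule

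*SAP*

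**What the plan says.** SAP section 9.5.2 lists a single food-effect comparison: "Regimen <C or D> (delafloxacin Powder for Oral Suspension Fed) vs Regimen B (delafloxacin Powder for Oral Suspension Fasted) (assessment of food effect". SAP Table 1 fixes Regimen B at 450 mg suspension, fasted. The parameters are log Cmax, AUC(0-last) and AUC(0-inf). Section 9.5.2 mentions dose correction only for the dose-proportionality analysis. Subjects enter the food-effect analysis "if they have data for both the fed and fasted state in regimens included in the comparison above".

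SAP section 9.1.1 defines relative bioavailability without dose correction and lists the food comparison as "450 mg delafloxacin Powder for Oral Suspension fed (test) vs delafloxacin Powder for Oral Suspension fasted (reference".

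The protocol is more specific about dose. Section 15.4 plans the analysis "to assess for the effects of food on delafloxacin Powder for Oral Suspension regimens administered at the same dose level". Section 8.1 defines a subject evaluable for food effect as one who has "received delafloxacin Powder for Oral Suspension in the fed and fasted state, at the same dose level".

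The protocol also describes how a fed Regimen D can arise. Under section 8.1, Regimen C may be an alternative dose given fasted. For Regimen D, "the Investigator and Sponsor will decide whether to continue to evaluate the dose level selected for Regimen C following a high-fat breakfast" is then one of the two options. Section 8.2.2 adds that Regimens C and D "will only be administered in the fed state if the selected dose level has previously been administered in the fasted state". Protocol Table 2 shows Regimen D as XX or YY mg, while Regimen C is shown as 450 or XX mg. SAP section 5.1 repeats the Regimen D decision, and SAP section 13.2 declares no change to the planned analyses.

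**The concern.** The SAP bullet allows the fed regimen to be C or D but names only one fasted comparator. If C is fasted at a new dose and D is that dose fed, C is the fasted arm that isolates food. Following the bullet literally sets D against B, so both dose and prandial state differ between the arms, and the parameters carry no dose correction.

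Food effect is a secondary objective reported as a GMR with a 90% CI. On this branch a pure dose difference could be read as a food effect, or could cancel a real one. Cancellation is plausible for Cmax: protocol section 5.3.2 reports that food lowers Cmax of existing delafloxacin, and a D dose above 450 mg would push the ratio to B the other way.

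The inclusion rule inherits the problem, because it is tied to the same comparison. A subject with usable C fasted and D fed data but no Regimen B data is evaluable under protocol section 8.1, yet the SAP would leave that subject out. A subject with B and D but no usable C would be included without being evaluable under the protocol. Replacements could create the first case, since under protocol section 8.4 "Replacement subjects enrolled will be dosed with the next planned regimen of the withdrawn subject".

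**Working it through.** The documents give no figure of their own on this point: there is no sample size calculation and no assumed variability. The check therefore traces the permitted paths and then sizes the consequence.

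**Paths to a fed suspension regimen (protocol 8.1, 8.2.2, Table 2)**

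| Path | Fed regimen | Same-dose fasted partner | Comparator in SAP 9.5.2 | Agrees? |
|---|---|---|---|---|
| C is 450 mg fed | C | B (450 mg) | B | Yes |
| C is XX mg fasted, D is XX mg fed | D | C (XX mg) | B (450 mg) | No |

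The second row is the fed Regimen D that section 8.1 describes. If C were already 450 mg fed, giving the C dose fed again as D would only repeat it.

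**Size of the shift**

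Inputs:
- Regimen B dose of 450 mg (SAP Table 1).
- Dose range for C and D of 300 to 600 mg (protocol 8.2.2).
- Exposure proportional to dose. Protocol 5.3.2 reports this over 50 to 1600 mg for Cmax and 200 to 1600 mg for AUC. It is an assumption for this suspension.

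With D dose *d* and true fed/fasted ratio *R*:

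expected GMR of D fed to B fasted = R × d/450

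| d (mg) | Displayed GMR when R = 1 | True R that would display as 100% (450/d) |
|---|---|---|
| 300 | 300/450 = 66.67% | 150% |
| 400 | 400/450 = 88.89% | 112.5% |
| 500 | 500/450 = 111.11% | 90% |
| 600 | 600/450 = 133.33% | 75% |

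The comparison of D fed with C fasted has an expected GMR of 100% at every dose when R = 1.

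Mock Figure 14.2.4.1 draws lines at 80.00% and 125.00%, and a similar figure is planned for food effect. The dose ratio alone reaches those lines at 0.80 × 450 = 360 mg and 1.25 × 450 = 562.5 mg.

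**Illustrative intervals**

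For paired data under the SAP model (regimen fixed, subject random):

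90% CI = GMR × exp(± t(0.95, n−1) × s_w × √(2/n)), with s_w = √(ln(1 + CV²))

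The within-subject CV is not given in the documents. A range of 15% to 30% is assumed, centred on the expected GMR with no food effect.

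| Comparison | n = 16, CV 15% | n = 16, CV 30% | n = 12, CV 30% |
|---|---|---|---|
| D 300 mg fed vs B | 60.78–73.12% | 55.58–79.97% | 53.76–82.68% |
| D 600 mg fed vs B | 121.56–146.25% | 111.15–159.94% | 107.51–165.35% |
| D fed vs C fasted, same dose | 91.17–109.69% | 83.36–119.96% | 80.64–124.01% |

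Every interval against B in this table excludes 100%, although food has no effect in these scenarios. Every same-dose interval includes it.

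**The case against.** The best reply is that nobody would run the wrong contrast. The protocol states the same-dose rule twice. The SAS code leaves the contrast as a placeholder. Mock Table 14.2.3.3 uses generic dose and prandial-state headings for both columns, so a comparison of unequal doses would at least be visible. An analyst who reads the protocol would probably choose Regimen C. That is a fair reason to keep the severity moderate. It does not correct the bullet: SAP section 16 calls the mock outputs illustrative, and the next bullet in 9.5.2 shows that the authors could leave a comparator open, as they do with Regimen X for dose proportionality. The re-evaluation clause in section 9.5.1 concerns deviations from planned treatment, and this branch is planned.

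Several narrower objections stand in part:

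- **Trigger.** The branch needs a non-450 mg fasted C, a decision to run Period 4, and D fed at the C dose. The 67% and 133% figures are the ends of the dose range.
- **80% and 125% lines.** They are not a decision rule. The study is exploratory and tests no formal hypothesis, so the 360 and 562.5 mg thresholds describe how a plot would look, not a planned conclusion.
- **Replacements.** Protocol section 8.4 goes on to allow a replacement to receive other regimens needed for a valid comparison, including fed versus fasted. The limit of four replacements is therefore a ceiling on those affected.
- **Relative bioavailability.** A footnote in SAP section 9.1.3 provides additional food-effect ratios where possible, so the 450 mg item in 9.1.1 is not the only provision.

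**Conclusion.** The concern holds. The SAP's food-effect comparator is correct when C is 450 mg fed. It conflicts with protocol sections 8.1 and 15.4 when D is fed at a Regimen C dose other than 450 mg. On that branch, with no food effect, the literal GMR is expected to lie between 67% and 133% over the 300 to 600 mg range, depending on dose. This rests on dose proportionality, which is reported for earlier oral delafloxacin and not yet shown for this suspension. The conflict in wording does not depend on that assumption. Because the protocol already contains the right rule, this is a SAP error on a conditional branch and not a missing analysis. It should be fixed, and it says nothing about which dose or prandial state ought to be chosen.

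**What to change.** In SAP section 9.5.2, define the food-effect comparison as the fed suspension regimen versus the fasted suspension regimen given at the same dose level. Regimen B is then the comparator whenever the fed dose is 450 mg, and Regimen C whenever D is fed at a different dose that C gave fasted. Include subjects with usable fed and fasted data at that dose level, matching the evaluability definition in protocol section 8.1. Reword the food item in the relative bioavailability list of SAP section 9.1.1 in the same way, without the 450 mg restriction.

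The cost is a few lines of SAP text. Protocol section 15.4 requires the analysis plan to be signed before database lock, so the change belongs before that point, and preferably before the Regimen D decision. On the affected branch the C fasted and D fed data would already be collected, so no extra dosing or sampling is needed.

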9.5.3 Statistical Figures for Analysis of Pharmacokinetic Data

A plot of geometric mean ratios (90% CI) obtained from the statistical model to evaluate relative bioavailability and food effect will be produced for each of the PK parameters: Cmax, AUC(0-last), and AUC(0-inf), with bars representing the 90% CIs. A scatter plot will be overlayed onto the graph to show the individual ratio values.

9.6 Interim PK Analysis

The details of the planned interim PK analysis are described in this section. However, as the analysis will be performed in real time, it may be necessary to change the planned analysis in response to the emerging data.

Summary tables and figures for the interim PK analysis will be presented in an Interim PK Summary Report after being exported from WinNonlin. The formatting of this output will differ slightly from the final PK output, which will be produced using SAS to include in the CSR.

The interim PK analysis will be performed on QC-checked delafloxacin concentration data in plasma using nominal sampling times and doses.

The following PK parameters will be calculated for the interim analysis:

delafloxacin Tablet (reference)

Tlag, Tmax, Cmax, AUC(0-24), AUC(0-last), AUC(0-inf), T1/2

delafloxacin Powder for Oral Suspension (test)

Tlag, Tmax, Cmax, AUC(0-24), AUC(0-last), AUC(0-inf), T1/2, Frel Cmax, Frel AUC(0-last), Frel AUC(0-inf)

10 Taste Assessments

Taste will be assessed for each of the delafloxacin Powder for Oral Suspension (i.e., test) regimens administered using a questionnaire (example provided in [Appendix 2](#)) immediately following test IMP administration.

Questions 1 and 2 within the questionnaire will ask subjects to rate the acceptability of 7 taste attributes (smell, sweetness, bitterness, flavour, mouth feel/texture, and aftertaste), as well as overall acceptability on a 9-point scale. For the purposes of continuous data summaries categories on the taste scale will be assigned numerical equivalents from 1-9 where 1 = 'Dislike extremely' to 9 = 'Like extremely'. No assumption will be made for summary statistics considered missing (i.e. recorded as "not detectable") but they will be included as a category.

